### 9.2.26. Shift table by multiple of normal range for laboratory parameters

#### For Stage 1:

|    |                 | Baseline |                 |             |               |                 |          |          |
|----|-----------------|----------|-----------------|-------------|---------------|-----------------|----------|----------|
|    |                 | <0.5*LLN | >0.5*LLN - <LLN | Normal      | >ULN - <2*ULN | >2*ULN - <3*ULN | 3*ULN    | Missing  |
| D5 | <0.5*LLN        | 0 (0.0%) | 0 (0.0%)        | 0 (0.0%)    | 0 (0.0%)      | 0 (0.0%)        | 0 (0.0%) | 0 (0.0%) |
|    | >0.5*LLN - <LLN | 0 (0.0%) | 1 (0.5%)        | 0 (0.0%)    | 0 (0.0%)      | 0 (0.0%)        | 0 (0.0%) | 0 (0.0%) |
|    | Normal          | 0 (0.0%) | 0 (0.0%)        | 117 (56.3%) | 1 (0.5%)      | 0 (0.0%)        | 0 (0.0%) | 0 (0.0%) |
|    | >ULN - <2*ULN   | 0 (0.0%) | 0 (0.0%)        | 0 (0.0%)    | 0 (0.0%)      | 0 (0.0%)        | 0 (0.0%) | 0 (0.0%) |
|    | >2*ULN - <3*ULN | 0 (0.0%) | 0 (0.0%)        | 0 (0.0%)    | 0 (0.0%)      | 0 (0.0%)        | 0 (0.0%) | 0 (0.0%) |
|    | >3*ULN          | 0 (0.0%) | 0 (0.0%)        | 0 (0.0%)    | 0 (0.0%)      | 0 (0.0%)        | 0 (0.0%) | 0 (0.0%) |
|    | Missing         | 0 (0.0%) | 0 (0.0%)        | 0 (0.0%)    | 0 (0.0%)      | 0 (0.0%)        | 0 (0.0%) | 0 (0.0%) |

Bowker's symmetry test: p=xx.xxx

<Same template for D11, D15, M3, M6, M12, M18.>

For Stage Intermediate: same templates as above.

For Stage 2: same templates as above.

For Stage 1 and Intermediate: same templates as above..

For all stages (total): same templates as above.

Note: the same template will be provided for TSH using the following classes: <0.5\*LLN, [0.5\*LLN to <LLN, Normal, >ULN to 2\*ULN], >2\*ULN).

### 9.2.27. Shift table according to lower and upper limits of normal range for laboratory parameters

#### For Stage 1:

| Baseline           |          |             |          |          |
|--------------------|----------|-------------|----------|----------|
| Haemoglobin (g/dL) | <LLN     | Normal      | >ULN     | Missing  |
| D5 <LLN            | 0 (0.0%) | 0 (0.0%)    | 0 (0.0%) | 0 (0.0%) |
| Normal             | 0 (0.0%) | 117 (56.3%) | 0 (0.0%) | 0 (0.0%) |
| >ULN               | 0 (0.0%) | 0 (0.0%)    | 0 (0.0%) | 0 (0.0%) |
| Missing            | 0 (0.0%) | 0 (0.0%)    | 0 (0.0%) | 0 (0.0%) |

Bowker's symmetry test: p=x.xxx

| Baseline           |          |             |          |          |
|--------------------|----------|-------------|----------|----------|
| Haemoglobin (g/dL) | <LLN     | Normal      | >ULN     | Missing  |
| D11 <LLN           | 0 (0.0%) | 0 (0.0%)    | 0 (0.0%) | 0 (0.0%) |
| Normal             | 0 (0.0%) | 117 (56.3%) | 0 (0.0%) | 0 (0.0%) |
| >ULN               | 0 (0.0%) | 0 (0.0%)    | 0 (0.0%) | 0 (0.0%) |
| Missing            | 0 (0.0%) | 0 (0.0%)    | 0 (0.0%) | 0 (0.0%) |

Bowker's symmetry test: p=x.xxx

| Baseline           |          |             |          |          |
|--------------------|----------|-------------|----------|----------|
| Haemoglobin (g/dL) | <LLN     | Normal      | >ULN     | Missing  |
| D15 <LLN           | 0 (0.0%) | 0 (0.0%)    | 0 (0.0%) | 0 (0.0%) |
| Normal             | 0 (0.0%) | 117 (56.3%) | 0 (0.0%) | 0 (0.0%) |
| >ULN               | 0 (0.0%) | 0 (0.0%)    | 0 (0.0%) | 0 (0.0%) |
| Missing            | 0 (0.0%) | 0 (0.0%)    | 0 (0.0%) | 0 (0.0%) |

Bowker's symmetry test: p=x.xxx

| Baseline           |          |             |          |          |
|--------------------|----------|-------------|----------|----------|
| Haemoglobin (g/dL) | <LLN     | Normal      | >ULN     | Missing  |
| M3 <LLN            | 0 (0.0%) | 0 (0.0%)    | 0 (0.0%) | 0 (0.0%) |
| Normal             | 0 (0.0%) | 117 (56.3%) | 0 (0.0%) | 0 (0.0%) |
| >ULN               | 0 (0.0%) | 0 (0.0%)    | 0 (0.0%) | 0 (0.0%) |
| Missing            | 0 (0.0%) | 0 (0.0%)    | 0 (0.0%) | 0 (0.0%) |

Bowker's symmetry test: p=x.xxx

| Baseline           |          |             |          |          |
|--------------------|----------|-------------|----------|----------|
| Haemoglobin (g/dL) | <LLN     | Normal      | >ULN     | Missing  |
| M6 <LLN            | 0 (0.0%) | 0 (0.0%)    | 0 (0.0%) | 0 (0.0%) |
| Normal             | 0 (0.0%) | 117 (56.3%) | 0 (0.0%) | 0 (0.0%) |
| >ULN               | 0 (0.0%) | 0 (0.0%)    | 0 (0.0%) | 0 (0.0%) |
| Missing            | 0 (0.0%) | 0 (0.0%)    | 0 (0.0%) | 0 (0.0%) |

Bowker's symmetry test: p=x.xxx

| Baseline           |          |             |          |          |
|--------------------|----------|-------------|----------|----------|
| Haemoglobin (g/dL) | <LLN     | Normal      | >ULN     | Missing  |
| M12 <LLN           | 0 (0.0%) | 0 (0.0%)    | 0 (0.0%) | 0 (0.0%) |
| Normal             | 0 (0.0%) | 117 (56.3%) | 0 (0.0%) | 0 (0.0%) |
| >ULN               | 0 (0.0%) | 0 (0.0%)    | 0 (0.0%) | 0 (0.0%) |
| Missing            | 0 (0.0%) | 0 (0.0%)    | 0 (0.0%) | 0 (0.0%) |

Bowker's symmetry test: p=x.xxx

| Baseline           |          |             |          |          |
|--------------------|----------|-------------|----------|----------|
| Haemoglobin (g/dL) | <LLN     | Normal      | >ULN     | Missing  |
| M18 <LLN           | 0 (0.0%) | 0 (0.0%)    | 0 (0.0%) | 0 (0.0%) |
| Normal             | 0 (0.0%) | 117 (56.3%) | 0 (0.0%) | 0 (0.0%) |
| >ULN               | 0 (0.0%) | 0 (0.0%)    | 0 (0.0%) | 0 (0.0%) |
| Missing            | 0 (0.0%) | 0 (0.0%)    | 0 (0.0%) | 0 (0.0%) |

Bowker's symmetry test: p=x.xxx

|    |         | Baseline |             |          |          |
|----|---------|----------|-------------|----------|----------|
|    |         | <LLN     | Normal      | >ULN     | Missing  |
| D5 | <LLN    | 0 (0.0%) | 0 (0.0%)    | 0 (0.0%) | 0 (0.0%) |
|    | Normal  | 0 (0.0%) | 117 (56.3%) | 0 (0.0%) | 0 (0.0%) |
|    | >ULN    | 0 (0.0%) | 0 (0.0%)    | 0 (0.0%) | 0 (0.0%) |
|    | Missing | 0 (0.0%) | 0 (0.0%)    | 0 (0.0%) | 0 (0.0%) |

Bowker's symmetry test: p=x.xxx

[figure not shown]
**For Stage Intermediate:** same template as above.

**For Stage 2:** same template as above.

**For Stage 1 and Intermediate:** same template as above.

**For all stages (total):** same template as above.

#### 9.2.28. Scatterplot between baseline and visit X for laboratory parameters

**9.2.29. Descriptive analysis for body weight (kg) at baseline, at each time points and changes from baseline at each time point**

**For Stage 1:**

|          | Value at visit |     |      |      |        |      |      |      |      |      | Change from baseline |        |      |      |      |      |      |      |      |      |
|----------|----------------|-----|------|------|--------|------|------|------|------|------|----------------------|--------|------|------|------|------|------|------|------|------|
|          | Missing        | N   | Mean | SD   | Median | Q1   | Q3   | Min  | Max  | Mean | SD                   | Median | Q1   | Q3   | Min  | Max  |      |      |      |      |
| Baseline | xx             | xxx | xx.x | xx.x | xx.x   | xx.x | xx.x | xx.x | xx.x | .    | .                    | .      | .    | .    | .    | .    | .    | .    | .    | .    |
| D5       | xx             | xxx | xx.x | xx.x | xx.x   | xx.x | xx.x | xx.x | xx.x | xx.x | xx.x                 | xx.x   | xx.x | xx.x | xx.x | xx.x | xx.x | xx.x | xx.x | xx.x |
| D11      | xx             | xxx | xx.x | xx.x | xx.x   | xx.x | xx.x | xx.x | xx.x | xx.x | xx.x                 | xx.x   | xx.x | xx.x | xx.x | xx.x | xx.x | xx.x | xx.x | xx.x |
| D15      | xx             | xxx | xx.x | xx.x | xx.x   | xx.x | xx.x | xx.x | xx.x | xx.x | xx.x                 | xx.x   | xx.x | xx.x | xx.x | xx.x | xx.x | xx.x | xx.x | xx.x |
| M3       | xx             | xxx | xx.x | xx.x | xx.x   | xx.x | xx.x | xx.x | xx.x | xx.x | xx.x                 | xx.x   | xx.x | xx.x | xx.x | xx.x | xx.x | xx.x | xx.x | xx.x |
| M6       | xx             | xxx | xx.x | xx.x | xx.x   | xx.x | xx.x | xx.x | xx.x | xx.x | xx.x                 | xx.x   | xx.x | xx.x | xx.x | xx.x | xx.x | xx.x | xx.x | xx.x |
| M12      | xx             | xxx | xx.x | xx.x | xx.x   | xx.x | xx.x | xx.x | xx.x | xx.x | xx.x                 | xx.x   | xx.x | xx.x | xx.x | xx.x | xx.x | xx.x | xx.x | xx.x |
| M18      | xx             | xxx | xx.x | xx.x | xx.x   | xx.x | xx.x | xx.x | xx.x | xx.x | xx.x                 | xx.x   | xx.x | xx.x | xx.x | xx.x | xx.x | xx.x | xx.x | xx.x |

**For Stage Intermediate:** same template as above.

**For Stage 2:** same template as above.

**For Stage 1 and Intermediate:** same template as above.

**For all stages (total):** same template as above.

**9.2.30. Descriptive analysis of relative change from baseline in body weight (%) at each time points**

|   | Stage 1
(N=XX) | Stage                  | Stage 1 and            | Stage 2
(N=XX) | Total
(N=XX) |
|---|-------------------|------------------------|------------------------|-------------------|-----------------|
|   |                   | Intermediate
(N=XX) | Intermediate
(N=XX) |                   |                 |
| Relative changes from baseline in body weight (%) at D5 |                   |                        |                        |                   |                 |
| Non-mising  | xx                | xx                     | xx                     | xx                | xx              |
| Missing   | xx                | xx                     | xx                     | xx                | xx              |
| <= -10%   | xx (xx.x)         | xx (xx.x)              | xx (xx.x)              | xx (xx.x)         | xx (xx.x)       |
| > -10% and <= -5%                                       | xx (xx.x)         | xx (xx.x)              | xx (xx.x)              | xx (xx.x)         | xx (xx.x)       |
| > -5% and < 5%  | xx (xx.x)         | xx (xx.x)              | xx (xx.x)              | xx (xx.x)         | xx (xx.x)       |
| >= 5% and < 10%   | xx (xx.x)         | xx (xx.x)              | xx (xx.x)              | xx (xx.x)         | xx (xx.x)       |
| >= 10%  | xx (xx.x)         | xx (xx.x)              | xx (xx.x)              | xx (xx.x)         | xx (xx.x)       |

<same statistics for relative changes from baseline in body weight (%) at D11, D15, M3, M6, M12, M18>

## 10. KEY DERIVED VARIABLES

### 10.1. Outcome at 18 months

| Derivation algorithm for stage 1 and intermediate stage (month 18)   | Derivation algorithm for stage 2 (Month 18)  |
|--|--|
| 
Patient is → 1: Dead (any reason of death and any time between drug intake and M18) ⇒ Failure (stop)
         ↓
         Alive
         ↓
 Patient requires rescue medication for HAT at M18 or required it before (between drug intake and M18)
         → YES → 2: (definitive) Failure (stop)
         ↓
         NO rescue medication so far
         ↓
 Evidence of trypanosomes in any body fluid between drug intake and M18 visit ⇒ YES ⇒ 3: (definitive) Failure (stop)
         ↓
         NO observed trypanosomes
         ↓
 Patient Lost to follow-up at M18 (no survival information at M18 and later)
         → YES ⇒ 4: Failure (Stop) [a,b]
         ↓
         NO (the patient is not lost to follow-up)
         ↓
 Non-hemorrhagic lumbar puncture at M18 and WBC in CSF at M18 > 20 cells
         → YES ⇒ 5: Failure (stop)
         ↓
         NO (WBC in CSF at M18 ≤ 20 cells or no reliable data concerning WBC in CSF at M18)
         ↓
 Non-hemorrhagic lumbar puncture at M18 and WBC in CSF ≤ 20 cells
         → YES ⇒ 6: Success (stop)
         ↓
         NO (hemorrhagic CSF sample or no lumbar puncture at M18 for any reason)
         ↓
 No lumbar puncture at M18 or no reliable count of WBC in CSF at M18 but reliable number of WBC in CSF reported later (M24 or other additional visit)
         → YES ⇒ WBC in CSF > 20 ⇒ 7: Failure (Stop)
         → YES ⇒ WBC in CSF ≤ 20 ⇒ 8: Success (Stop)
         ↓
         NO (No lumbar puncture at M18 and no later reliable count of WBC in CSF)
 | 
Patient is → 1: Dead (any reason of death and any time between drug intake and M18) ⇒ Failure (stop)
         ↓
         Alive
         ↓
 Patient requires rescue medication for HAT at M18 or required it before (between drug intake and M18)
         → YES ⇒ 2: (definitive) Failure (stop)
         ↓
         NO rescue medication so far
         ↓
 Evidence of trypanosomes in any body fluid between drug intake and M18 visit ⇒ YES ⇒ 3: (definitive) Failure (stop)
         ↓
         NO observed trypanosomes
         ↓
 Patient Lost to follow-up at M18 (no survival information at M18 and later)
         → YES ⇒ 4: Failure (Stop) [a,b]
         ↓
         NO (The patient is not lost to follow-up)
         ↓
 Non-hemorrhagic lumbar puncture at M18 and WBC in CSF at M18 > 20 cells
         → YES ⇒ 5: Failure (stop)
         ↓
         NO (WBC in CSF at M18 ≤ 20 cells or no reliable data concerning WBC in CSF at M18)
         ↓
 Non-hemorrhagic lumbar puncture at M18 and WBC in CSF ≤ 20 cells
         → YES ⇒ 6: Success (stop)
         ↓
         NO (hemorrhagic CSF sample or no lumbar puncture at M18 for any reason)
         ↓
 No lumbar puncture at M18 or no reliable count of WBC in CSF at M18 but reliable number of WBC in CSF reported later (M24 or other additional visit)
         → YES ⇒ WBC in CSF > 20 ⇒ 7: Failure (Stop)
         → YES ⇒ WBC in CSF ≤ 20 ⇒ 8: Success (Stop)
         ↓
         NO (No lumbar puncture at M18 and no later reliable count of WBC in CSF)
 |

| Derivation algorithm for stage 1 and intermediate stage (month 18)   | Derivation algorithm for stage 2 (Month 18)  |
|--|--|
| 
Earlier (before M18) unfavorable outcome: increase of WBC in CSF at M6 or M12 with respect to EOH
 
⇒ YES ⇒ 9: Failure (stop)
 
↓
 
NO (no information or no earlier unfavorable assessment)
 
↓
 
Patient has clinical signs or symptoms at M18 evoking a failure
 
⇒ YES ⇒ 10: Failure (stop)
 
↓
 
NO (no clinical signs or symptoms evoking a relapse at M18)
 
↓
 
WBC in CSF ≤ 20 at M12 or absence of LP at M12 and for both cases no increase WBC in CSF at M6 with respect to EOH and no sign and symptoms at M18 evoking a relapse:
 
⇒ YES ⇒ 11: Success (stop) [b]
 
↓
 
NO (at least one criterion not met)
 
↓
 
Patient refused all post treatment lumbar punctures
 
⇒ YES ⇒ 12: Failure (stop) [a,b]
 
↓
 
All other cases ⇒ 13. Failure
 | 
Earlier (before M18) unfavorable outcome: WBC in CSF > 50 at M6 or WBC in CSF > 20 at M12 or increasing between M6 and M12
 
⇒ YES ⇒ 9: Failure (stop)
 
↓
 
NO (no information or no earlier unfavorable assessment)
 
↓
 
Patient has clinical signs or symptoms at M18 evoking a failure
 
⇒ YES ⇒ 10: Failure (stop)
 
↓
 
NO (no clinical signs or symptoms evoking a relapse at M18)
 
↓
 
WBC in CSF ≤ 20 at M12 or in absence of LP at M12 and for both cases WBC in CSF ≤ 50 at M6 and no signs and symptoms at M18 evoking a relapse:
 
⇒ YES ⇒ 11: Success (Stop) [b]
 
↓
 
NO (at least one criterion not met)
 
↓
 
Patient refused all post treatment lumbar punctures
 
⇒ YES ⇒ 12: Failure (Stop) [a,b]
 
↓
 
All other cases ⇒ 13. Failure
 |

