##### **Endpoints in Patients with Early- or Intermediate-stage HAT**

Two efficacy endpoints will be used for patients with early- and intermediate-stage HAT: the outcome at 12 months and the outcome at 18 months after receiving treatment. A patient will be considered as a success at 12 months if the patient is alive with no evidence of trypanosomes in any body fluid and if the CSF

WBC is equal to or less than 20/ $\mu$ L. A patient with no parasitological evidence of relapse, but with a CSF WBC above 20/ $\mu$ L or who, in the Investigator's opinion, requires rescue treatment, will be considered as a relapse. A patient who refuses the lumbar puncture at 12 months will be classified as a probable cure (success) in the absence of any clinical signs or symptoms suggestive of THA or with another obvious aetiology, provided that the outcome was favourable, i.e. a CSF WBC equal to or less than 5/ $\mu$ L, at 6 months. Death for any reason, patients lost to follow-up and not retrieved or patients with no post-treatment lumbar puncture will be considered as failures, with the exception of patients who fled the region due to armed conflict or natural disaster. For memory, patients who fled the region due to armed conflict or natural disaster will not be included in the mITT population and will therefore not be taken into account in the calculation of the success rate. A patient with early- or intermediate-stage HAT will be considered as a **success** at 18 months if the CSF WBC is equal to or below 20/ $\mu$ L and in the absence of trypanosomes, rescue treatment and signs or symptoms suggestive of a relapse. If the patient does not have a lumbar puncture at 18 months, the outcome at 6 months or at 12 months will be used.

A patient with early- or intermediate-stage HAT will be considered as a success at 6 months and at 12 months if the CSF WBC is equal to or less than 20/ $\mu$ L and in the absence of trypanosomes, rescue treatment and signs or symptoms suggestive of a relapse. If the patient does not have a lumbar puncture at 6 months, the outcome at 12 months and, if necessary, at 18 months will be used. If the patient does not have a lumbar puncture at 12 months, the outcome at 18 months will be used and, if necessary, the outcome at 6 months will be used. If no post-treatment lumbar punctures were performed, the outcome will be considered as unfavourable.

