12 months	12 months $\pm 4$ weeks	
 
Patient alive with no evidence of trypanosomes in any body fluid and CSF WBC <math>\leq 20/\mu\text{L}</math>
 
CSF WBC between 20 and <math>50/\mu\text{L}</math>, and lower as compared to prior value(s)
 
	
 
CSF WBC <math>> 20/\mu\text{L}</math> and non-significant increase from a clinical standpoint in relation to prior value(s)
 
Any reason prompting the Investigator to request an additional follow-up visit
 
	
 
CSF WBC <math>> 20/\mu\text{L}</math> and significant increase from a clinical standpoint in relation to prior value(s)
 
Neurological signs or symptoms leading to use of rescue treatment
 
	
 
Evidence of trypanosomes in any body fluid
 

18 months	18 months $\pm 4$ weeks	
 
Patient alive with no evidence of trypanosomes in any body fluid and CSF WBC <math>\leq 20/\mu\text{L}</math>
 
Patient with no signs of HAT and who refuses to undergo lumbar puncture and who, in the opinion of the Investigator does not require rescue treatment or an additional follow-up visit
 
	
 
Any reason prompting the Investigator to request an additional follow-up visit
 
	
 
CSF WBC <math>> 20/\mu\text{L}</math>
 
Neurological signs or symptoms leading to use of rescue treatment
 
	
 
Evidence of trypanosomes in any body fluid
 

Any discrepancy between the clinical features and laboratory findings may also be an uncertain outcome, or any situation that leads the Investigator or the study team to consider that an additional follow-up visit is required to decide whether or not to provide rescue treatment.

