#### 6.4.4. At Unscheduled Visits

If a relapse of HAT is suspected on the basis of physical examination findings or CSF WBC at any visit, the patient must attend a return visit within 1 to 3 months, at the discretion of the Investigator.

The patient must also return to the investigational centre if s/he does not feel well, even if there is no apparent relationship with treatment or HAT.

The following assessments will be performed:

- Karnofsky performance status;
- Height, weight and BMI;
- Vital signs: body temperature, blood pressure, heart rate, respiratory rate and general status;
- Physical and neurological examinations (including signs and symptoms of HAT since the previous visit);
- Investigation of any concomitant condition that may have led to the visit;
- Testing for *T.b. gambiense* in blood and lymph, if indicated;
- CSF sampling, only if symptoms suggesting relapse are present;
- Laboratory safety assessments at the discretion of the Investigator (see Appendix 3 – Laboratory Tests; p84) – if possible, samples will be collected in the morning from patients in the fasting state:

- Haemoglobin
- Haematology: WBC, platelet count
- Biochemistry: albumin, ALP, ALT, AST, BUN, chloride, creatinine, glucose, potassium, sodium, calcium, total bilirubin, bicarbonates and total protein;
- Thyroid function test, if indicated: TSH, free T3, free T4;
- Additional safety assessments, e.g. ECG or urine analysis, may be performed at the discretion of the Investigator;
- Urine pregnancy test for women of child-bearing potential, at the discretion of the Investigator;
- Collection of concomitant medication and adverse events.

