## 6. DEFINITION OF ENDPOINTS

### 6.1. Primary efficacy endpoint

#### Primary endpoint for patients with Stage 2 HAT

The primary endpoint is the outcome (success or failure) at the 18 months visit according to the adapted WHO criteria:

- Success is defined as a cure or a probable cure (cf. algorithm in [Section 10.1](#)).
- Failure is defined as a relapse, probable relapse, death for any reason (up to and including the 18 months visit) or use of rescue medication (up to and including the 18 months visit) or lost to follow-up for any reason (up to and including the 18 months visit) or refusal of all post-treatment lumbar puncture (up to and including the 18 months visit) or had unfavourable outcome earlier than M18 or sign and symptoms evoking a relapse at M18 (cf. algorithm in [Section 10.1](#)).

Note: data review committee composed of those involved in the study conduct and data processing will check before database lock the status of patients (success or failure) using the algorithm presented in [Section 10.1](#).

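### SAP 10.1 awards 18-month success on a CSF count of 20 or below without testing for signs of relapse: this contradicts the protocol for early/intermediate-stage patients, and for late-stage patients it leaves SAP 6.1 and 10.1 giving different answers

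*SAP*

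**What the plan says.** SAP 10.1 is a numbered sequence in two columns, one for stage 1/intermediate and one for stage 2. Each decision ends in a stop. Steps 1 to 5 remove deaths, rescue, trypanosomes, loss to follow-up and an M18 count above 20. The rescue step reads "Patient requires rescue medication for HAT at M18 or required it before" and the parasite step reads "Evidence of trypanosomes in any body fluid between drug intake and M18 visit". Step 6 then gives success on "Non-hemorrhagic lumbar puncture at M18 and WBC in CSF ≤ 20 cells". Steps 7 and 8 use a later count, but only under the condition "No lumbar puncture at M18 or no reliable count of WBC in CSF at M18 but reliable number of WBC in CSF reported later". Signs and symptoms at M18 are tested at step 10.

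Three other places bear on the same patient:

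- SAP 6.1 (stage 2 primary endpoint) includes among the failures a patient who "had unfavourable outcome earlier than M18 or sign and symptoms evoking a relapse at M18".
- Protocol 2.2.2 makes 18-month success in early/intermediate-stage patients depend on a count of 20 or below "in the absence of trypanosomes, rescue treatment and signs or symptoms suggestive of a relapse".
- Protocol 2.2.1 defines late-stage success as alive, free of trypanosomes and with a count of 20 or below. It has no signs criterion for a patient who has the lumbar puncture.

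Protocol Table 1 has an uncertain category at 18 months, and its closing note covers situations in which the team considers that "an additional follow-up visit is required to decide whether or not to provide rescue treatment". Under Protocol 6.4.4, when relapse is suspected, "the patient must attend a return visit within 1 to 3 months".

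**The concern.** Because step 6 stops the sequence, step 10 never sees a patient with a reliable M18 count of 20 or below. Such a patient may have signs evoking a relapse, no trypanosomes and no decision yet on rescue. That is the patient whom Table 1 would call uncertain and send for another visit. SAP 10.1 records a success, and nothing found at that further visit can change it.

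The classification of an endpoint should not depend on which section the programmer follows. The trial has no numerical success rule (Protocol 9.6.2, SAP 8.7). The observed rate and its lower confidence limit are read against historical data, so single patients show in the result. For the patients concerned, omitting the signs test can only raise the success rate.

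**Working it through.** **1. The same patients through each text.** SAP 10.1 was applied in its printed order, taking a count of 12 wherever an M18 lumbar puncture was done.

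| Patient | SAP 10.1, either column |
|---|---|
| A. Count 12, signs at M18; additional visit shows trypanosomes, count 80, rescue given | Step 6: success |
| B. Count 12, signs at M18, no trypanosomes, no rescue decision, nothing later | Step 6: success |
| C. No M18 puncture, same signs, no later count | Step 10: failure |
| D. No M18 puncture, same signs, later count 80 | Step 7: failure |
| F. Count 12, signs, rescue required at M18 | Step 2: failure |
| G. Count 12, signs, trypanosomes at M18 | Step 3: failure |

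C assumes no unfavourable earlier count, which would be a failure at step 9 in any case. F and G show that step 6 does not rest on the count in isolation, since rescue or parasites by M18 have already been removed. The gap is patients A and B. A against D shows that a later count of 80 is read only when the M18 count is missing.

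**2. Patient B by document.**

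| Text | Stage 1/intermediate | Stage 2 |
|---|---|---|
| SAP 10.1 | Success | Success |
| Protocol 2.2.2 (18 months) | Not a success | Does not apply |
| Protocol 2.2.1 | Does not apply | Success, unless the investigator considers rescue required |
| SAP 6.1, read literally | Does not apply | Failure |

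SAP Section 11 lists changes to adverse-event counting, stage wording and the yardstick. It says nothing about the cohort 2 signs condition.

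**3. Possible safeguards.** The data review committee in SAP 6.1 checks status with the 10.1 algorithm itself. The time-window rule that takes the latest visit is excluded for the primary and secondary endpoints (SAP 7.5). Footnotes [a] and [b] are not attached to step 6 at M18, so the best-case and fair-case analyses leave it alone. The remaining analyses in SAP 8.6.1.2 change the analysis set or drop missing outcomes. None reclassifies patient A or B.

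**4. The additional visit.** The SAP's theoretical M18 date is D548. Three months at the SAP's 91 days gives 548 + 91 = D639, the upper limit of its own M18 window. The descriptive tables of blood, lymph and CSF findings do use that window and take the latest visit. They could therefore show patient A as positive at M18 while the primary table counts a success. SAP 6.3 (time to failure, stage 2) counts a decision to use rescue at any time after dosing, so A would be an event there.

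**5. Size.** The Jeffreys limits are the 2.5% and 97.5% quantiles of Beta(x + 0.5, n − x + 0.5). The plan's own figures reproduce: 138/155 gives 83.40 to 93.23, width 9.83 (stated 83.4 to 93.2, 9.8), and 146/155 gives 89.67 to 97.09, width 7.42 (stated 89.7 to 97.1, 7.4).

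The documents do not give the number k of patients like A or B, so k is an assumption. If k late-stage patients move from success to failure:

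| k | Starting from 146/155 | Starting from 151/155 |
|---|---|---|
| 0 | 94.2% (89.7–97.1) | 97.4% (94.0–99.1) |
| 1 | 93.5% (88.9–96.6) | 96.8% (93.1–98.8) |
| 2 | 92.9% (88.1–96.2) | 96.1% (92.2–98.4) |
| 3 | 92.3% (87.3–95.7) | 95.5% (91.3–98.0) |
| 5 | 91.0% (85.7–94.7) | 94.2% (89.7–97.1) |

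Each patient moves the rate by 1/155 = 0.65 points and the lower limit by about 0.8 to 0.9 points. In cohort 2 each moves it by 1/50 = 2 points, for example from 46/50 = 92% to 45/50 = 90%. For scale, a success rate of 94% in 155 patients means 155 × 0.06 = 9.3 failures, and 89% means 155 × 0.11 = 17.1.

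**The case against.** The strongest reply concerns stage 2. Protocol 2.2.1 and the first favourable entry at 18 months in Table 1 have no signs criterion. In 2.2.1 symptoms matter only when the final puncture is refused, which is roughly where step 10 sits. Steps 1 to 6 implement that definition. A reader might infer that the SAP has departed from the protocol's primary endpoint; on this criterion it has not, and Section 11 had no stage 2 change to list.

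SAP 6.1 also refers to 10.1, and its clause can be read as naming steps 9 and 10 in order. Its first half, taken literally, would fail a patient with a count above 20 at M12 and 20 or below at M18, who is a success under 2.2.1. That supports reading 6.1 as a summary. It does not remove the problem, because 6.1 states no such limit.

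A reader might also infer that the primary analysis must count any relapse proven at the additional visit. The documents do not support that. SAP 6.1 bounds death, rescue and loss to follow-up at the 18-month visit, and the yardstick is reported at 18 months. Reading later findings only in recalled patients would make follow-up uneven. Nor does the handling of later data run only towards success: step 7 turns a missing M18 count into a failure if a later count exceeds 20.

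None of this reaches cohort 2. Table 1 carries no signs criterion there either, but Table 1 is a visit-by-visit clinical classification, whereas Protocol 2.2.2 defines the endpoint and states the condition.

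**Conclusion.** The point holds in three parts of different weight.

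- **Stage 1/intermediate:** step 6 contradicts the protocol's 18-month definition, and the change is undeclared. This is a secondary endpoint.
- **Stage 2:** step 6 agrees with the protocol. The defect is that SAP 6.1, read literally, and SAP 10.1 classify the same patient differently on the primary endpoint.
- **After M18:** the fixed landmark is a legitimate choice. What is missing is an analysis showing whether relapse found at an additional visit requested at M18 would alter the result.

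The effect per patient is known (0.65 or 2 points), but the number of patients is not, and it may be zero. The tabulated shifts rest on assumed values of k and on 155 and 50 patients in the denominators. They do not show that the success rate is materially overstated.

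**What to change.** 1. In the stage 1/intermediate column of SAP 10.1, add to step 6 the condition that there are no signs or symptoms evoking a relapse at M18, using the same derivation that step 10 already needs.
2. For stage 2, reconcile SAP 6.1 with SAP 10.1 and Protocol 2.2.1 before database lock, so that one classification is stated. Report the other as a sensitivity analysis.
3. Keep the M18 landmark for the primary analysis. Add a sensitivity analysis that counts as failures those patients whose additional visit, requested because the M18 outcome was uncertain under Table 1, shows trypanosomes or leads to rescue.
4. Report how many patients each alternative reclassifies, and record the changes in the SAP.

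The cost is SAP wording and a few lines of derivation. No new data are needed: Protocol 6.1 requires unscheduled visits to be recorded in the CRF, and Protocol 5.4 puts rescue on the end-of-study page. The downside is that the reported success rate may fall slightly.
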